- Treatment adherence questions, based on modified versions of the Multiple Sclerosis Treatment Adherence Questionnaire (MS-TAQ); data to be collected via ePRO at baseline (modified for self-injectables to assess adherence during last previous injectable DMD treatment) and at the end of Months 1, 2, 13, and 14 (modified for cladribine tablets); a Spanish translation is available to patients.
- Proportion of patients experiencing a relapse. For this study, a relapse will be defined as determined and recorded by the investigator and information on the definition used by the investigator will be collected (see Section 9.1.2.1 for a guide on definition).
- Proportion of patients with relapse associated with hospitalization (relapse as primary diagnosis or reason for hospitalization). For this study, a relapse will be defined as determined by the investigator (see Section 9.1.2.1 for a guide on definition).
- Proportion of patients with relapse associated with glucocorticoid use. For this study, a relapse will be defined as determined by the investigator (see Section 9.1.2.1 for a guide on definition).
- Assessment of previous treatment for MS:
 - Previous DMD(s) received for MS prior to study enrollment, since MS diagnosis
 - Reasons for discontinuation of previous DMD(s)
- Proportion of patients who discontinue cladribine tablets
 - Reason for discontinuation of cladribine tablets
 - Elapsed time to discontinuation after first dose
 - Number of doses and % of planned doses (as per USPI) received
 - Subsequent treatment chosen following discontinuation of cladribine tablets
- Assessment of concomitant MS medications used during study period
- The ARR based on the last 24 months (or since MS diagnosis, if diagnosis <24 months) prior to the start of treatment with cladribine tablets (retrospective data). For this study, a relapse will be defined as determined by the investigator (see Section 9.1.2.1 for a guide on definition).

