9.2.2 Definition of Study Cohorts and Description of Treatments

The study will have a single cohort that consists of all patients enrolled in the study who received at least 1 dose of cladribine tablets. All treatment and other medical decisions will be made by the investigator.

All study patients are anticipated to receive marketed cladribine tablets as per investigator discretion and as per US approved label: 3.5 mg/kg body weight over 2 years, administered as 1 treatment course of 1.75 mg/kg per year. Each treatment course consists of 2 treatment weeks, 1 at the beginning of the first month and 1 at the beginning of the second month of the respective year. Each treatment week consists of 4 or 5 days on which a patient receives 10 mg or 20 mg (1 or 2 tablets) as a single daily dose, depending on body weight. Since prescribing is determined by the investigator as per standard of care and according to the USPI, the benefits and risks to patients in being in the study are not different than the benefits and risks to patients taking cladribine tablets as per standard of care and according to the USPI in the general population.

Following completion of the 2 treatment courses, do not administer treatment during the next 2 years as stated in the USPI.

As per USPI, ALC values need to be normal at the initiation of cladribine tablets in Year 1, and ALC results need to indicate \geq 800 cells per microliter at the start of the Year 2 treatment course. If necessary, the Year 2 treatment course should be delayed for up to 6 months to allow for recovery of lymphocytes to \geq 800 cells per microliter. If this recovery takes more than 6 months, the patient should not receive further treatment with cladribine tablets.

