#### **Additional Subgroup Analysis Populations**

	Analysis Population		
Analyses	Full Analysis Set	Per Protocol Analysis Set	Safety Analysis Set*
Baseline Assessments (baseline characteristics of patients initiating cladribine tablets, baseline PRO data, baseline laboratory data, baseline data on previous MS DMD use, relapses during the previous 2 years [or since MS diagnosis if diagnosis <24 months], baseline MRI data, retrospective MRI data	~	~	V
and past treatment adherence)			,
Compliance and Exposure	~		~
Primary Endpoint Analysis (ARR over the 24-month period)	$\checkmark$	$\checkmark$	~
Secondary Endpoints Analysis: The ARR over the 12-Month follow- up period , Sensitivity analyses of the ARR, ARR during the last 24 months (or since MS diagnosis if diagnosis <24 months) before starting cladribine tablets, Other relapse analyses	✓ 	~	×

	Analysis Population		
Analyses	Full Analysis Set	Per Protocol Analysis Set	Safety Analysis Set*
Treatment patterns (MS treatment during the last 2 years (or since MS diagnosis if diagnosis <24 months) before transition to cladribine tablets, concomitant treatment for MS, follow-up treatment in case of discontinuation of cladribine tablets)	~		~
PROs and treatment adherence	$\checkmark$		$\checkmark$
Analyses of MRI imaging data	✓		✓
JCV antibody status	✓		✓
Analyses of ALC as well as complete blood count and lymphocyte subsets, if available	✓	$\checkmark$	✓
Concomitant medications	✓		✓
Safety	✓		✓

Subgroup analyses will be performed for the primary endpoint on subgroups as defined below.

Subgroups:

The following subgroups will be defined:

- Patients completing the 24-month study
- Patients not completing the 24-month study (i.e., lost to follow-up, withdrawing consent, protocol deviations)
- Patients not completing treatment (i.e., completing Year 1 treatment but not Year 2 treatment, or not completing both courses of treatment each year)
- Type of MS at screening: RRMS, aSPMS, PPMS, CIS
- Patients diagnosed with MS <24 months before transitioning to cladribine tablets
- Centers
  - Pooling of centers: Because of the high number of participating centers and the anticipated small number of patients in each centers data will be pooled across centers, and the factor centers will not be considered in statistical models or for subgroup analyses.

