#### Time to event data

Time to event data will be summarized descriptively as continuous data and using Kaplan-Meier (KM) analysis. Data summarization will include:

- Plot of KM curve with number at risk
- KM estimates with CI at fixed timepoints (e.g., every 6 months) (with number at risk/ failed)
- Median survival times with CI, and first quartile (Q1) and third quartile (Q3).

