The number and percentage of patients who started another MS treatment after discontinuation of cladribine tablets will be reported (using the number of patients who discontinue cladribine tablets as denominator).

Reasons for discontinuation of cladribine tablets will be collected and for each reason, the corresponding number and percentage of patients will be reported (using the number of patients who discontinue cladribine tablets as denominator).

A listing of concomitant MS medications started after discontinuation of cladribine tablets will be provided. The following variables will be reported:

- Patient ID
- Medication name
- Visit
- Dose
- Unit
- Frequency
- Route of administration
- Start Date / Ongoing (Yes/No) / Stop Date
- Last study treatment administration date

The elapsed time to discontinuation of cladribine tablets will be calculated as:

*elapsed time to discontinuation of cladribine tablets = Date of discontinuation of cladribine tablets – Date of first study dose* 

It will be summarized as a continuous variable and also reported through a KM analysis. The 'Last study treatment administration date' according to the Treatment Termination form will be used as date of discontinuation of cladribine tablets (both for patients early discontinuing the treatment and for patients completing the treatment; for patients completing the treatment this will be a censoring date).

Number of doses and % of planned doses (as per USPI) received will be summarized descriptively.

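### SAP 13 dates discontinuation at the last tablet, so a patient who completes Year 1 on schedule and never starts Year 2 is scored as stopping at about Month 1, before any dose has been omitted

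*SAP*

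**What the plan says.** Protocol 9.1.2.2 lists "Elapsed time to discontinuation after first dose" under the secondary outcome on patients who discontinue cladribine tablets. It does not say which date counts as discontinuation.

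SAP 13 supplies the definition. Elapsed time is "Date of discontinuation of cladribine tablets – Date of first study dose". The last administration date "according to the Treatment Termination form will be used as date of discontinuation of cladribine tablets", and this applies "both for patients early discontinuing the treatment and for patients completing the treatment". The two groups differ only in status: "for patients completing the treatment this will be a censoring date". No censoring rule is given for anyone else.

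SAP 13 asks for both a continuous summary and a Kaplan-Meier analysis of this variable. SAP 9 has the same general rule ("Time to event data will be summarized descriptively as continuous data", plus Kaplan-Meier) and gives estimates every 6 months as its example.

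Protocol 9.2.2 sets the calendar. Each yearly course has two treatment weeks, "1 at the beginning of the first month and 1 at the beginning of the second month" of that year, each with 4 or 5 dosing days. Year 2 may be delayed by up to 6 months. SAP 8.2 counts a patient "completing Year 1 treatment but not Year 2 treatment" among those not completing treatment.

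**The concern.** Last dose is a natural stopping date for a drug taken continuously. Here every patient, including those who go on to complete, takes no tablets between about Month 1 and Month 12. A patient in that interval is fully on plan, and the last-dose date says nothing about whether treatment has been abandoned.

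The rule gives nearly the same time to two different patients: one who stops in the second week of the Year 1 course, and one who finishes that course and is later not given Year 2. A reader of the curve would take both as early stopping. In a study of real-world treatment patterns, whether patients stop within a course or fail to receive the second one is much of what this outcome should show.

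Two further problems come from the same sentence:

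- Completers are also given a value, their own last-dose date. The continuous summary is not restricted to discontinuers, so as worded it can average event times with censoring times.
- Only completers have a censoring rule. A patient who dies, withdraws or is lost between courses could be counted as discontinuing near Month 1.

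**Working it through.** The plan states no figure for this outcome, so there is none to reproduce. The check applies the SAP formula to the protocol calendar.

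**Inputs**
- Formula: last dose date minus first dose date, with no added day (SAP 13).
- Second treatment week starts one month after the first, taken as 28 to 31 days; 4 or 5 dosing days per week (Protocol 9.2.2).
- Year 2 due at about Month 12; delay of up to 6 months, so the window closes at about Month 18 (Protocol 9.2.2).
- 1 month = 30.4375 days (SAP 9).
- Year-1-only share: not in the documents; 10, 20 and 30% assumed.

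**Step 1: Year-1-only patient, on schedule.**
- Shortest: 28 + (4 − 1) = 31 days; 31 / 30.4375 = 1.02 months.
- Longest: 31 + (5 − 1) = 35 days; 35 / 30.4375 = 1.15 months.

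The due date and the window close lie at Months 12 and 18, so the scored time is about 11 to 17 months before the point at which the course was due or no longer possible.

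**Step 2: completer.** Year 2 on time: 12 + 1.02 to 12 + 1.15 = 13.02 to 13.15 months. With the full delay: 19.02 to 19.15 months. These are censoring times.

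**Step 3: Kaplan-Meier, 100 hypothetical patients.** S(t) is the product of (1 − d/n) over event times up to t. For a 20% share under the SAP rule, 20 events occur at 1.1 months with 100 at risk: 1 − 20/100 = 0.80. There are no later events, and completers are censored at 13.1.

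| Rule (20% share) | Month 2 | Month 6 | Month 12 | Month 18 |
|---|---|---|---|---|
| SAP: event at 1.1, completers censored at 13.1 | 0.80 | 0.80 | 0.80 | 0.80 |
| Event at 12, completers censored at 24 | 1.00 | 1.00 | 0.80 | 0.80 |
| Event at 18, completers censored at 24 | 1.00 | 1.00 | 1.00 | 0.80 |
| Event at 18, completers still censored at 13.1 | 1.00 | 1.00 | 1.00 | 0.00 |

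With shares of 10% or 30%, 0.80 becomes 0.90 or 0.70. The last row is 0.00 for any share: once completers leave at 13.1, only the 20 discontinuers are at risk, so 1 − 20/20 = 0. Moving the event date without also changing the completers' censoring would make the curve worse.

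**Step 4: continuous summary.** If completers are included, the 20% example gives a mean of 0.20 × 1.1 + 0.80 × 13.1 = 10.7 months. Restricted to discontinuers, it is 1.1 months under the SAP date. The wording does not say which is meant.

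**The case against.** **The rule is deliberate and observable.** The SAP modification history records that the definition was added in version 3.0. Last dose needs no imputation, and the protocol does not define the date. This is an analysis choice, not a contradiction between documents. That stands, but the choice still gives a misleading time for a drug given in two courses a year apart.

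**When patients really decide to stop is unknown.** A reader might infer that nearly all discontinuation happens at Months 12 to 18, and that the correct curve is therefore close to 1 until then. The documents do not support this. Protocol 11.4 lists reasons for stopping, such as pregnancy, infection or renal impairment, that can arise at any time after the Year 1 course, and a switch to another DMD can too. No decision date is listed among the variables in Protocol 9.3. The near-flat early curve in the re-dated rows above results from the assumed event dates and is not an estimate.

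**Other outputs limit the harm.** SAP 13 also gives reasons for discontinuation, the percentage of planned doses received, an exposure listing by visit and a listing of later MS drugs with start dates. SAP 10.1 gives disposition by reason. A reader would not depend on the curve alone. However, none of these outputs tabulates discontinuation by stage.

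**Some material is not visible.** SAP 5 maps this outcome to Sections 11.3 and 12, and Section 12 is redacted. A supporting summary may be there. The Treatment Termination form is not provided either, so its field is read by its plain name. The rule in SAP 13 is nevertheless explicit.

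**Completers may not be meant to enter the continuous summary.** This is possible. The text neither includes nor excludes them, so it needs a sentence.

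**Conclusion.** The point holds for timing. Under SAP 13, a Year-1-only patient who took the first course on schedule is an event at 1.0 to 1.15 months, before any dose was omitted. If the second Year 1 week was taken late, the scored time moves by the same amount. The curve drops by the whole Year-1-only share just after Month 1. The size of that drop rests on the assumed shares.

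A reader might infer that discontinuation itself is miscounted or that the primary result is affected. Neither follows. The number and percentage discontinuing do not depend on this date, and the primary ARR uses Time on Study. The final Kaplan-Meier level is also unchanged when all events precede the completers' censoring.

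The outcome is descriptive and single-arm. The change is worth making because it is cheap and the outcome is named in the protocol, but it does not threaten the study's main conclusion.

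**What to change.** In SAP 13:

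1. Add a table of discontinuation by stage: during the Year 1 course, between courses, during the Year 2 course. This needs no imputed date and gives most of the missing information.
2. Restrict the continuous summary to patients who discontinued.
3. For patients who completed Year 1 and did not start Year 2, date the event at the earlier of (a) the recorded start of another MS DMD and (b) the due date of the omitted course. For (b), use nominal Month 12, or the end of the protocol's delay window where a delay is documented, and use the other date as a sensitivity analysis. Taking the earlier of (a) and (b) prevents a late switch from being scored after the course was due. Censor at death or study exit if that comes first. Carry completers event-free to the end of follow-up; the event date and this censoring rule must change together.
4. Keep the present version as supplementary, labelled *time to last dose*.

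The cost is SAP wording, one derivation and one table. Cladribine dates and other-DMD start dates are already collected (Protocol 9.3). The downside is an imputed date, and so an artificial step in the curve, for patients with no recorded switch. The sensitivity analysis shows how much that convention matters.

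### SAP 13 gives treatment completers a time to discontinuation: read literally, the continuous summary describes course length, and Kaplan-Meier estimates after about Month 13 rest on few patients or none

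*SAP*

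**What the plan says.** Protocol 9.1.2.2 lists "Elapsed time to discontinuation after first dose" as a sub-item of the proportion of patients who discontinue cladribine tablets, and SAP 5 keeps that nesting.

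SAP 13 computes the variable as "Date of discontinuation of cladribine tablets – Date of first study dose". It fixes the first of these dates: "The 'Last study treatment administration date' according to the Treatment Termination form will be used as date of discontinuation of cladribine tablets". The rule applies "both for patients early discontinuing the treatment and for patients completing the treatment; for patients completing the treatment this will be a censoring date".

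On reporting, SAP 13 says: "It will be summarized as a continuous variable and also reported through a KM analysis". SAP 9 sets the same pair of summaries for every such variable: "Time to event data will be summarized descriptively as continuous data and using Kaplan-Meier (KM) analysis". It gives 6-monthly KM estimates as an example, with the number at risk and failed.

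SAP 13 names the FAS for its summaries. It uses discontinuers as the denominator for reasons for stopping and for subsequent MS treatment, but states no such limit for elapsed time.

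**The concern.** The point concerns completers. The dating of early stoppers is taken as the SAP gives it.

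**Continuous summary.** A censoring flag has no effect on a mean, median or quartile. If completers are included, patients who never discontinued contribute a time to discontinuation equal to the length of their treatment. The protocol nests the outcome under patients who discontinue, so such a summary would answer a different question.

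**KM analysis.** Censoring assumes that the patient could still have the event later. Under Protocol 9.2.2 no cladribine is planned for the two years after the second course, so within this study a completer cannot discontinue. Under Protocol 9.2.3 the patient is still followed, so event-free status is known. Removing completers at their last dose leaves the later part of the curve to the few patients whose Year 2 course started late. The resulting estimate may then disagree with the crude percentage reported beside it.

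**Working it through.** The documents give no discontinuation rate, delay rate or KM value, so there is no planned figure to reproduce. The schedule comes from the documents; all patient counts below are assumptions.

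**1. When each type of patient has the last dose**

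Inputs:
- Protocol 9.2.2: "Each treatment course consists of 2 treatment weeks, 1 at the beginning of the first month and 1 at the beginning of the second month", in both treatment years; 4 or 5 days per treatment week (5 used, so the last day is 4 days after the first); Year 2 delayed by at most 6 months.
- SAP 9: 30.4375 days per month, 365.25 days per year.

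| Patient | Days from first dose | Months | Status in KM |
|---|---|---|---|
| Stops after Year 1 week 1 | 4 | 0.1 | event |
| Completes Year 1, never starts Year 2 | 30.4375 + 4 = 34.4 | 1.1 | event |
| On time, stops after Year 2 week 1 | 365.25 + 4 = 369.3 | 12.1 | event |
| On-time completer | 365.25 + 30.4375 + 4 = 399.7 | 13.1 | censored |
| 6-month delay, stops after Year 2 week 1 | 369.25 + 182.6 = 551.9 | 18.1 | event |
| 6-month delay, completer | 399.7 + 182.6 = 582.3 | 19.1 | censored |

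**2. Continuous summary**

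Assume 100 patients, in whole days: 80 completers at day 399 (365 + 30 + 4), and 20 stoppers (5 at day 4, 12 at day 34, 3 at day 369).

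- All patients: mean = (80×399 + 5×4 + 12×34 + 3×369)/100 = 33,455/100 = 334.6 days; median 399 days.
- Stoppers only: mean = (20 + 408 + 1,107)/20 = 1,535/20 = 76.8 days; median 34 days.

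The all-patient median is the on-time completer's value whenever more than half complete on time, whatever the stoppers did.

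**3. KM with completers censored at last dose**

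Assume N = 100: 3 stop after Year 1 week 1, 15 after Year 1 week 2, and 2 on-time patients after Year 2 week 1. Nobody is censored before 13.1 months.

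- Survival at Month 12: (97/100)×(82/97) = 0.82, so 18% have discontinued, equal to the crude share by then.
- Survival after 12.1 months: 0.82×(80/82) = 0.80, so 20%.
- No later event: KM stays at 20.0%, equal to the crude 20.0%.
- One late stopper at Month 16.1 (4-month delay) with r patients at risk: KM = 1 − 0.80×(1 − 1/r), against a true 21/100 = 21.0%.

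| r at risk | KM | Excess (points) |
|---|---|---|
| 25 | 23.2% | 2.2 |
| 20 | 24.0% | 3.0 |
| 10 | 28.0% | 7.0 |
| 5 | 36.0% | 15.0 |

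After the last completer is censored (Month 13.1 with no delays, up to about Month 19.1 with a 6-month delay) the risk set is empty.

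**4. How often it bites**

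Each setting used 2,000 simulated cohorts of 100, with 3% stopping after Year 1 week 1, 15% never starting Year 2, and 3% of the rest stopping after Year 2 week 1.

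| Delayed | SD of Year 2 start | Mean KM | Mean true share |
|---|---|---|---|
| 0% | 0.5 month | 20.4% | 20.4% |
| 0% | 1 month | 21.5% | 20.4% |
| 10% | 0.5 month | 24.3% | 20.6% |
| 20% | 0.5 month | 24.1% | 20.5% |

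In the last two rows the median excess is zero, while the 95th percentile is about 21 and 18 points. A minority of studies drives the average.

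**5. After the change**

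With completers kept at risk to Month 24, the estimate equals the crude proportion in every scenario of step 3 (20.0% or 21.0%).

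**The case against.** **A discontinuers-only summary may be what is meant.** The variable is named for discontinuation, the protocol and SAP 5 nest it under patients who discontinue, and a censoring date has meaning only for the KM analysis. This is a plausible reading, so a reader who infers that the plan is certain to report a wrong value goes further than the text. But SAP 13 gives completers a date of discontinuation, names the FAS, and restricts neighbouring summaries to discontinuers explicitly while leaving this one unrestricted. A programmer following the text would include completers.

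**Later KM estimates are not inflated as a matter of course.** A reader might infer that they always are. The SAP's own dating rule prevents this: patients who never start Year 2 count at about Month 1, and on-time Year 2 stoppers at about Month 12, both before on-time completers leave. An excess needs a patient with a late or delayed Year 2 start who stops after that. With 20 to 25 such patients at risk, one event adds only 2 to 3 points. This stands, and it limits the KM part to a conditional risk.

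**There are safeguards.** SAP 9 asks for numbers at risk, so a nearly empty risk set would be visible. The 6-monthly times are only an example. The crude number and percentage are reported, and SAP 9 calls all tests exploratory. These measures help a careful reader detect the problem, but they do not make the censoring rule suitable.

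**Conclusion.** The point holds in two parts of different strength.

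**Continuous summary.** As written, it is not limited to discontinuers. Taken literally, its median is about 13.1 months whenever more than half of patients complete on time. That result needs only the dosing schedule and the completion share. The 399 against 34 days (median) and 335 against 77 days (mean) also rest on the assumed 80/20 split and stopping times.

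**KM analysis.** The censoring rule is unsuitable because completion precludes the event while follow-up continues, but its numerical effect is conditional. Month 6 and 12 estimates are essentially unaffected, and with no late event KM equals the crude proportion. One late stopper can add from about 2 points (25 at risk) to 15 points (5 at risk) under the assumed counts. Independently of those counts, if Year 2 delays stay within 6 months, a Month 24 KM estimate has no patient at risk behind it.

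This affects one descriptive sub-item of a secondary outcome. The primary ARR and the crude discontinuation percentage are untouched. The change should be made, but it is not critical to the study's main conclusion.

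**What to change.** In SAP 13:

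- (a) State that the continuous summary of elapsed time to discontinuation covers only patients who discontinued cladribine tablets.
- (b) In the time-to-event analysis, keep completers event-free in the risk set to the end of their follow-up (Month 24, or Month 30 if Year 2 is delayed). Alternatively, report a cumulative incidence with treatment completion as a competing event.

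With complete follow-up, either choice under (b) makes the Month 24 estimate agree with the crude proportion.

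The cost is two sentences in SAP 13 and a changed censoring date (or a competing-event code) in one program. No new data are needed, since the last-dose and end-of-study dates are already used elsewhere in the SAP.
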